  - f. PD-L1 expression Tumor Proportion Score (TPS)  $\geq$  1% for NSCLC and Combined Proportion Score (CPS)  $\geq$  1% for all other tumor types
  - g. A 28-day washout period after the completion of programmed death-1 (PD-1)/PD-L1 therapy
  - h. Patients should have no more than 5 prior lines of therapies
  - i. If the patients have progressed on treatment with prior PD-1/L1 inhibitor administered either as monotherapy or in combination with other therapies, additional following criteria must be met:

- have received at least 2 doses of the PD-1/L1 inhibitor;
- have been on a continuous regimen of the PD-1/L1 inhibitor for at least 4 months without disease progression;
- have demonstrated radiographic disease progression after PD-1/L1

j. Patients who have had more than 1 prior PD-1/L1 inhibitor may be considered after discussion with the Sponsor's Medical Monitor

6. Cohort 2 - Pre-treatment fresh tumor biopsies and paired treatment fresh tumor biopsies will be collected from at least 5 patients. Biopsy must be excisional, incisional, or core. Fine needle aspiration is insufficient. Waiver of biopsy samples must be discussed with Sponsor's Medical Monitor. NOTE: CD73 enzymatic activity and assessment of proteins in the adenosine pathway (e.g., CD73, A2A receptor, and whole genome gene expression profiles) will be assessed in fresh tumor biopsies. Samples will be collected prior to dosing and processed and shipped within 24 hours according to a separate laboratory manual. The fresh tumor biopsies require testing for the following infectious diseases: Hepatitis B, Hepatitis C, Tuberculosis, HIV, Syphilis, and COVID-19. Testing must be completed within 28 days of tumor biopsy collection and confirmed to be negative.

7. Willingness and ability to consent for self to participate in study and the ability to comply with scheduled visits, treatment plan, laboratory tests, and other study procedures

8. Patients who received prior PD-1/PD-L1 checkpoint inhibitor or prior CTLA-4 inhibitor therapy may enroll to Cohort 2 if they did not experience Grade 3 immune-related toxicity (applies to all tumor types except ovarian cancer patients)

9. At least one measurable lesion as defined by RECIST 1.1

10. Resolution of all acute adverse events resulting from prior cancer therapies to National Cancer Institute (NCI) Common Terminology Criteria for Adverse Events (CTCAE) v5.0 Grade  $\leq$  1 or baseline (except alopecia or neuropathy)

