  - f. PD-L1 expression Tumor Proportion Score (TPS)  $\geq$  1% for NSCLC and Combined Proportion Score (CPS)  $\geq$  1% for all other tumor types

- g. A 28-day washout period after the completion of programmed death-1 (PD-1)/PD-L1 therapy
- h. Patients should have no more than 5 prior lines of therapies
- i. If the patients have progressed on treatment with prior PD-1/L1 inhibitor administered either as monotherapy or in combination with other therapies, additional following criteria must be met:
  - have received at least 2 doses of the PD-1/L1 inhibitor;
  - have been on a continuous regimen of the PD-1/L1 inhibitor for at least 4 months without disease progression;
  - have demonstrated radiographic disease progression after PD-1/L1
- j. Patients who have had more than 1 prior PD-1/L1 inhibitor may be considered after discussion with the Sponsor's Medical Monitor.

6. Cohort 2 - Pre-treatment fresh tumor biopsies and paired treatment fresh tumor biopsies will be collected from at least 5 patients. Biopsy must be excisional, incisional, or core. Fine needle aspiration is insufficient. Waiver of biopsy samples must be discussed with Sponsor's Medical Monitor. NOTE: CD73 enzymatic activity and assessment of proteins in the adenosine pathway (e.g., CD73, A2A receptor, and whole genome gene expression profiles) will be assessed in fresh tumor biopsies. Samples will be collected prior to dosing and processed and shipped within 24 hours according to a separate laboratory manual. The fresh tumor biopsies require testing for the following infectious diseases: Hepatitis B, Hepatitis C, Tuberculosis, HIV, Syphilis, and COVID-19. Testing must be completed within 28 days of tumor biopsy collection and confirmed to be negative.

7. Willingness and ability to consent for self to participate in study and the ability to comply with scheduled visits, treatment plan, laboratory tests, and other study procedures

8. Patients who received prior PD-1/PD-L1 checkpoint inhibitor or prior CTLA-4 inhibitor therapy may enroll to Cohort 2 if they did not experience Grade 3 immune-related toxicity (applies to all tumor types except ovarian cancer patients)

9. At least one measurable lesion as defined by RECIST 1.1

10. Resolution of all acute adverse events resulting from prior cancer therapies to National Cancer Institute (NCI) Common Terminology Criteria for Adverse Events (CTCAE) v5.0 Grade  $\leq 1$  or baseline (except alopecia or neuropathy)

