## 5.2 Exclusion Criteria

Patients meeting any of the following criteria are not eligible for study participation:

1. Autoimmune disease requiring active treatment within the past twelve months (Note: vitiligo, type 1 diabetes mellitus, residual hypothyroidism due to autoimmune thyroiditis only requiring hormone replacement, and conditions not expected to recur in the absence of an external trigger are permitted)
2. Condition requiring systemic treatment with either corticosteroids (>10 mg daily prednisone equivalent) or other immunosuppressive medications within 14 days prior to study treatment (Note: inhaled and topical steroids, and adrenal replacement steroid doses > 10 mg daily prednisone equivalent, are permitted in the absence of active autoimmune disease.)
3. Has a history of (non-infectious) pneumonitis/interstitial lung disease that required steroids or has current pneumonitis/interstitial lung disease
4. Current treatment on another therapeutic clinical trial
5. Has received prior therapy with an anti-PD-1, anti-PD-L1, or anti-PD-L2 agent or with an agent directed to another stimulatory or co-inhibitory T-cell receptor (e.g. cytotoxic T-lymphocyte-associated protein 4 [CTLA-4], OX 40 [Tumor necrosis factor receptor superfamily, member 4 (TNFRSF4)], CD137 [tumor necrosis factor receptor superfamily member 9 (TNFRSF9)]) (only applies to ovarian cancer patients in Cohorts 1 and 2)
6. For ovarian patients in both cohorts:
  - a. Patients who progressed during or within 3 months of first line of platinum-based therapy
  - b. Patients with histologically non-epithelial tumors or ovarian tumors with low malignant potential (i.e., borderline tumors) or mucinous tumors
  - c. Patients with evidence of bowel obstruction requiring hospitalization and decompression within the past 30 days

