### 6.9 Dose Modification and Dose Delays

The treatment management guidelines including dose delay and dose modification of TJ004309 for hematological and non-hematological toxicities are provided in [Table 6](#) and [Table 7](#) respectively. Treatment management guidelines for Immune-Related Adverse Events (irAEs) are provided in [Table 8](#).

Dose delay up to 4 weeks is allowed for subjects with manageable AEs at the Investigator's discretion, e.g., Grade 4 or Grade 3 thrombocytopenia with Grade  $\geq 2$  bleeding, uncomplicated Grade 3 febrile neutropenia, and Grade 4 neutropenia. The Investigator can continue to withhold treatment for up to 12 weeks after the last dose based on the Investigator's medical judgement. If the subject has recovered to Grade  $\leq 1$  or baseline within 12 weeks, continue treatment of TJ004309 at the same dose level. Dose modification or withholding of doses other than as described in this section is not permitted.

If a Grade  $\geq 2$  toxicity recurs for the second time, the Investigator may discuss with the Sponsor whether resuming TJ004309 is appropriate considering the type and grade of the toxicity. If the agreement is to resume TJ004309, treatment can continue to be withheld for up to 12 weeks to allow the subject to recover to Grade  $\leq 1$  or baseline at the Investigator's discretion. If the subject recovers to Grade  $\leq 1$  or baseline within 12 weeks, continue treatment of TJ004309 at the same dose level. If the subject does not recover within 12 weeks, permanently discontinue TJ004309. The Investigator should always manage their subjects according to their medical judgment based on the clinical circumstances.

All dose modifications must be clearly documented in the subjects' source notes and Case Report Form (CRF).

Study treatment dose delays are permitted in the case of medical/surgical events or logistical reasons not related to study therapy (e.g., surgery, unrelated medical events, patient vacation, and/or holidays). Participants should be placed back on study therapy within 28 days of the scheduled interruption, unless otherwise discussed with the Sponsor. The reason for interruption should be documented in the patient's study record. All dose delays must be clearly documented in the patients' source notes and the eCRF.

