**Table 8: TJ004309 Treatment Management Guidelines for Immune-Related Adverse Events (irAEs)**

General instructions:

1. Severe and life-threatening irAEs should be treated with IV corticosteroid followed by oral steroids. Other immunosuppressive treatment should begin if the irAEs are not controlled by corticosteroids.
2. TJ004309 must be permanently discontinued if the irAE does not resolve or the corticosteroid dose is not  $\leq 10$  mg/day within 12 weeks of the last treatment.
3. The corticosteroid taper should begin when the irAE is  $\leq$  Grade 1 and continue tapering at least 4 weeks.
4. If TJ004309 has been withheld, TJ004309 may resume after the irAE decreased to  $\leq$  Grade 1 after corticosteroid taper.

irAEs	Toxicity Grade (CTCAE V5.0)	Action with TJ004309	Corticosteroid and/or other therapies	Monitoring and Follow-up
Pneumonitis	Grade 2	Withhold	Administer corticosteroids (initial dose of 1 to 2 mg/kg prednisone or equivalent) followed by taper Add prophylactic antibiotics for opportunistic infections	Monitor participants for signs and symptoms of pneumonitis Evaluate participants with suspected pneumonitis with radiographic imaging and initiate corticosteroid treatment
	Recurrent Grade 2, Grade 3 or 4	Permanently discontinue		
Diarrhea / Colitis	Grade 2 or 3	Withhold	Administer corticosteroids (initial dose of 1 to 2 mg/kg prednisone or equivalent) followed by taper	Monitor participants for signs and symptoms of enterocolitis (ie, diarrhea, abdominal pain, blood or mucus in stool with or without fever) and of bowel perforation (ie, peritoneal signs and ileus) Participants with $\geq$ Grade 2 diarrhea suspecting colitis should consider GI consultation and performing endoscopy to rule out colitis Participants with diarrhea/colitis should be advised to drink liberal quantities of clear fluids. If sufficient oral fluid intake is not feasible, fluid and electrolytes should be substituted via IV infusion
	Recurrent Grade 3 or Grade 4	Permanently discontinue		
AST or ALT elevation or Increased Bilirubin	Grade 2 a	Withhold	Administer corticosteroids (initial dose of 0.5 to 1 mg/kg prednisone or equivalent) followed by taper	Monitor with liver function tests (consider weekly or more frequently until liver enzyme value returned to baseline or is stable)

	Grade 3 b or 4 c	Permanently discontinue	Administer corticosteroids (initial dose of 1 to 2 mg/kg prednisone or equivalent) followed by taper	

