Type 1 diabetes mellitus (T1DM) or Hyperglycemia	New onset T1DM or Grade 3 or 4 hyperglycemia associated with evidence of β-cell failure	Withhold d	Initiate insulin replacement therapy for participants with T1DM  Administer antihyperglycemic in participants with hyperglycemia	Monitor participants for hyperglycemia or other signs and symptoms of diabetes
Hypophysitis	Grade 2	Withhold	Administer corticosteroids and initiate hormonal replacements as clinically indicated	Monitor for signs and symptoms of hypophysitis (including hypopituitarism and adrenal insufficiency)
	Grade 3 or 4	Withhold or permanently discontinue d		
Hyperthyroidism	Grade 2	Continue	Treat with nonselective beta-blockers (e.g., propranolol) or thionamides as appropriate	Monitor for signs and symptoms of thyroid disorders
	Grade 3 or 4	Withhold or permanently discontinue d		

Hypothyroidism	Grade 2, 3 or 4	Continue	Initiate thyroid replacement hormones (e.g., levothyroxine or liothyronine) per standard of care	Monitor for signs and symptoms of thyroid disorders
Nephritis: grading according to increased creatinine or acute kidney injury	Grade 2	Withhold	Administer corticosteroids (prednisone 1 to 2 mg/kg or equivalent) followed by taper	Monitor changes of renal function
	Grade 3 or 4	Permanently discontinue		
Neurological Toxicities	Grade 2	Withhold	Based on severity of AE administer corticosteroids	Ensure adequate evaluation to confirm etiology and/or exclude other causes
	Grade 3 or 4	Permanently discontinue		
Myocarditis	Grade 2, 3 or 4	Permanently discontinue	Based on severity of AE administer corticosteroids	Ensure adequate evaluation to confirm etiology and/or exclude other causes
Exfoliative Dermatologic Conditions	Suspected SJS, TEN, or DRESS	Withhold	Based on severity of AE administer corticosteroids	Ensure adequate evaluation to confirm etiology and/or exclude other causes
	Confirmed SJS, TEN, or DRESS	Permanently discontinue		
All other irAEs	Persistent Grade 2	Withhold		Ensure adequate evaluation to confirm etiology and/or exclude other causes

	Grade 3	Withhold or discontinue based on the event e	Based on severity of AE administer corticosteroids	
	Recurrent Grade 3 or Grade 4	Permanently discontinue		

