**Table 10: Adverse Event Severity Grading**

Grade	Non-CTCAE Severity	Definition
1	Mild	Asymptomatic or mild symptoms; clinical or diagnostic observations only; or intervention not indicated
2	Moderate	Minimal, local, or non-invasive intervention indicated; or limiting age-appropriate instrumental ADL b
3	Severe	Medically significant, but not immediately life-threatening; hospitalization or prolongation of hospitalization indicated; disabling; or limiting self-care ADL c
4	Life-Threatening	Urgent intervention indicated
5	Fatal	Results in patient's death

NCI CTCAE = National Cancer Institute Common Terminology Criteria for Adverse Events.

ADL= Activities of Daily Living

b Instrumental ADL refers to preparing meals, shopping for groceries or clothes, using the telephone, managing money, etc.

c Self -care ADL refer to bathing, dressing, and undressing, feeding self, using the toilet, taking medications, and not bedridden

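### Inclusion 8 bars a prior Grade 3 immune-related event but, as written, not a prior Grade 4 one; it should read Grade ≥3

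*Protocol*

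**What the plan says.** Protocol Section 5.1, inclusion 8, covers patients who have already had a PD-1/PD-L1 or CTLA-4 inhibitor. They "may enroll to Cohort 2 if they did not experience Grade 3 immune-related toxicity". The synopsis carries the same condition: "if they did not experience Grade 3 immune-related toxicity". Neither place adds a ≥ sign or any mention of Grade 4. The criterion applies to every Cohort 2 tumor type except ovarian cancer; exclusion 5 already keeps out ovarian patients with prior checkpoint therapy.

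The protocol treats Grade 4 as a separate grade. Table 10 labels it life-threatening and describes it as "Urgent intervention indicated", one step above severe. Table 8, on management of immune-related events, names Grade 4 where it is meant, for example "Recurrent Grade 3 or Grade 4" and "Grade 3 or 4 hyperglycemia associated with evidence of".

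**The concern.** An eligibility rule on past toxicity should get stricter as the past event gets worse. This one does not: it excludes the severe event and says nothing about the life-threatening one. Every patient in Cohort 2 receives atezolizumab with TJ004309, so a patient admitted through the gap is re-exposed to checkpoint inhibition after a life-threatening immune reaction to the same class or to a CTLA-4 inhibitor.

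The gap would also be hard to see afterwards. Section 10.2 makes the investigator responsible for enrolling only subjects who meet the criteria. A patient with only a Grade 4 event on record does meet inclusion 8 as written, so a deviation review against that criterion need not flag the case.

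The stake is patient safety. Error rates, endpoints and estimates are not involved.

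**Working it through.** There is no figure to reproduce. The check has three parts: apply the rule as written, compare it with how the protocol writes grades elsewhere, and look for another criterion that closes the gap.

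**1. Literal test of inclusion 8**

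| Prior immune-related event on record | As written | With Grade ≥3 |
|---|---|---|
| Grade 2 at worst | admitted | admitted |
| Grade 3 at worst | barred | barred |
| Grade 4, also recorded at Grade 3 | barred | barred |
| Grade 4 only | admitted | barred |

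Only the last row changes. SAP Section 9.1 records a change in severity as two separate events. If prior history were captured that way, an event that passed through Grade 3 would already fail. That rule governs on-study events, however, and nothing applies it to medical history.

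**2. How the protocol writes immune-related grades**

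Table 8 has 12 rows, of which 11 are graded (exfoliative skin conditions are not). Grade 4 is named in:
- 7 rows that pair Grades 3 and 4: pneumonitis, liver tests, type 1 diabetes/hyperglycemia, hypophysitis, hyperthyroidism, nephritis, neurological;
- 2 rows that list Grades 2, 3 and 4 together: hypothyroidism, myocarditis;
- 2 rows worded as "Recurrent Grade 3 or Grade 4": diarrhea/colitis and all other immune-related events.

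7 + 2 + 2 = 11, so all graded rows name it. In the last two rows a first Grade 3 event and a Grade 4 event lead to different actions. The first means withholding (or, for other events, withholding or discontinuing according to the event); the second means permanent discontinuation. In this protocol, then, Grade 3 without qualification can mean exactly Grade 3. Table 8 governs on-study dosing and is used here only as evidence of drafting convention.

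The convention is not uniform. Section 6.9 gives "uncomplicated Grade 3 febrile neutropenia, and Grade 4 neutropenia" as examples for dose delay, while Table 6 sets febrile neutropenia at Grade ≥3.

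**3. Other criteria that might stop the patient**

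| Criterion | What it catches | What it leaves |
|---|---|---|
| Inclusion 5(i) | Patients who progressed on a PD-1/L1 inhibitor must "have been on a continuous regimen of the PD-1/L1 inhibitor for at least 4 months without disease progression" | Later events, CTLA-4-only exposure, patients who stopped for toxicity |
| Inclusion 5(j) | Medical Monitor discussion after more than one PD-1/L1 inhibitor | Patients with one |
| Inclusion 10 | Unresolved events | Events back to Grade ≤1 or baseline |
| Inclusions 12(d)–(f), 13 | Incomplete renal or hepatic recovery; events neither resolved nor stable | Fully recovered patients |
| Exclusion 1 | Autoimmune disease treated in the past 12 months | Older events, and its note that "conditions not expected to recur in the absence of an external trigger are permitted" |
| Exclusion 2 | Systemic steroid or other immunosuppressive need within 14 days | Patients off treatment |
| Exclusion 3 | Current pneumonitis, or a history of it treated with steroids | Other organs |
| Exclusion 13 | Known active or chronic hepatitis, or cirrhosis | Other organs |
| Inclusion 11, exclusion 19 | Whatever the investigator judges unsuitable | No fixed rule |

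A patient with fully resolved Grade 4 colitis, off steroids, can pass every fixed rule in this list.

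**The case against.** The strongest reply is that no sensible investigator would read the criterion this way. Barring severe toxicity while admitting life-threatening toxicity is incoherent, so Grade 3 would be taken as a threshold. Inclusion 11 and exclusion 19 then give two further chances to decline the patient. This lowers the chance of harm, but it relies on readers correcting the text.

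The notation evidence can also be pressed. Besides febrile neutropenia, the chills row of Table 7 lists only Grade 3, and the diarrhea/colitis row there does not name a first Grade 4 event. The protocol therefore leaves Grade 4 unstated in other places, and Table 10 is meant for terms that CTCAE does not describe. These points stand. They show that the notation varies, which is a reason to make an eligibility threshold explicit.

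The other criteria narrow the group considerably, and the documents do not show that any such patient exists. That also stands, and it limits the size of the point.

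Finally, the amendment may come too late. SAP Section 4.1 says Part 2 was not started because Part 1 produced too few responses, and only an abbreviated report is planned. The documents do not say that Part 1 enrollment has closed, though it may have. In that case the forward-looking fix protects nobody in this trial; what remains is a retrospective check and a correction before reuse.

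**Conclusion.** The concern holds. As written, in both places, inclusion 8 admits a patient whose only recorded prior immune-related event was a resolved Grade 4 event, and no other criterion expressly bars that patient. It is best seen as a drafting slip that sets a wrong safety threshold.

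The effect is small. It reaches only non-ovarian Cohort 2 candidates (the cohort is up to 30 subjects, ovarian patients included) who had prior PD-1/L1 or CTLA-4 therapy and an immune event recorded at Grade 4 but never at Grade 3, who have recovered, and who pass the criteria listed above. The documents give no frequency for this group, so none is estimated.

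The conclusion rests on the literal reading. That the intent was Grade 3 or higher is an inference, though a strong one. Sample size and efficacy analyses do not change. Because the correction is so cheap and bears on patient safety, the sponsor should make it.

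**What to change.** In inclusion 8, replace Grade 3 with Grade ≥3 in Section 5.1 and in the synopsis, and leave the rest of the criterion alone. This restores the evident intent and removes no patient the sponsor is likely to have meant to enroll.

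If Part 1 enrollment has closed, check whether any enrolled Cohort 2 subject had a prior Grade 4 immune-related event, and correct the wording before it is used in another protocol.

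The cost is one symbol in two places, handled as a routine amendment with IRB approval before implementation (Sections 10.2 and 10.4.1). The SAP needs no change.

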- a. Agree to use at least 2 effective contraceptive methods (1 highly effective method in combination with a barrier method; oral, injectable, or implantable hormonal contraceptive; tubal ligation; intra-uterine device; barrier contraceptive with spermicide; or vasectomized partner), one of which must be barrier. Use of contraceptive methods lasts from date of ICF signature, throughout the study, and for up to 5 months following the last dose of TJ004309.
- b. Have a negative serum pregnancy test (sensitive of at least 25 mIU/ml) at Screening; and have a negative serum or urine pregnancy test within 72 hours prior to Cycle 1 Day 1 of study treatment (note that the screening serum pregnancy test can be used as the test prior to Day 1 study treatment if it is performed within the prior 72 hours)
- c. Avoid conceiving for 5 months after the last dose of TJ004309
- d. Avoid donation of ova from date of ICF signature until 5 months after the last dose of TJ004309
- e. Agree to ongoing urine pregnancy testing, if clinically indicated, during the study

16. Males must agree to use a condom (a latex condom is recommended) during sexual contact with a pregnant female or a female of childbearing potential, will avoid donation of sperm, or having a female partner conceive from date of ICF signature, while participating in the study, during dose interruptions, and for at least 5 months after the last dose of study treatment, even if he has undergone a successful vasectomy.

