17. Pregnancy or breastfeeding - Female patients must be surgically sterile (i.e.,  $\geq$  6 weeks following surgical bilateral oophorectomy with or without hysterectomy or tubal ligation) or be postmenopausal for at least one year or must agree to use effective contraception during the study and for 5 months following last dose of TJ004309. All female patients of reproductive potential must have a negative pregnancy test (serum or urine) within 72 hours prior to study treatment. Male patients must be surgically sterile or must agree to use effective contraception during the study and for 5 months following last dose of TJ004309
18. Patients with any severe infection within 4 weeks prior to initiation of study treatment, including, but not limited to, hospitalization for complications of infections should not be enrolled in the trial. Patients who required IV antibiotics or were treated with antiviral medications within this 4 week period should be discussed with the Sponsor Medical Monitor prior to enrollment
19. Other severe acute or chronic medical or psychiatric condition or laboratory abnormality that may increase the risk associated with study participation or may interfere with the interpretation of study results and, in the judgment of the Investigator, would make the patient inappropriate for this study

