#### 8.4.8 Pregnancy Reporting Requirement

A pregnancy event refers to a pregnancy of a female subject or a maternal pregnancy of a male patient during a clinical study or within 5 months after the patient's last dose of study drug. The Investigator will collect pregnancy information via the Pregnancy Reporting Form within 24 hours after becoming aware of the information.

Study drug must be discontinued immediately in the event of a pregnancy in a patient. The patient should be referred to an obstetrician/gynecologist experienced in reproductive toxicity for further evaluation and counseling.

The Investigator will follow the patient /patient's partner until completion of the pregnancy and provide this follow-up information using the same procedures as the initial reporting. Generally, the follow-up will be within 6 to 8 weeks following the estimated delivery date. Any termination of the pregnancy will be reported regardless of fetal status (presence or absence of anomalies) or indication for the procedure.

If the outcome of the pregnancy meets the criteria for immediate classification as an SAE ([Section 8.3.2](#)), then the Investigator should report it as such, and the Investigator needs to fill out an SAE reporting form and report to the Sponsor within 24 hours. Furthermore, all neonatal deaths that occurs within 30 days of birth should be reported, without regard to causality, as SAEs. In addition, any infant death after 30 days that the Investigator suspects is related to the in-utero exposure to the study drug should also be reported.

While pregnancy itself is not considered to be an AE or SAE, any pregnancy complication or elective termination of a pregnancy will be reported as an AE or SAE.

Any post-study pregnancy related SAE considered reasonably related to the study drug by the Investigator will be reported to the Sponsor or designee. While the Investigator is not obligated to actively seek this information in former study participants, he or she may learn of an SAE through spontaneous reporting.

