### 10.6.2 Fertile Males

A man is considered fertile after puberty (Tanner Stage II) unless permanently sterile by bilateral orchidectomy or vasectomy with medical assessment of surgical success.

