#### 10.6.7 Male Contraception Guidance

Males must agree to use a condom (a latex condom is recommended) during sexual contact with a pregnant female or a female of childbearing potential and will avoid donation of sperm or having a female partner conceive from the time of date of ICF signature, while participating in the study, during dose interruptions, and for at least 5 months after the last dose of study

treatment, even if he has undergone a successful vasectomy. Consider contraception for the FOCBP partner.

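### Women's contraception, conception and ova-donation limits are timed from the last TJ004309 dose only; time them from the later of the last TJ004309 and last atezolizumab dose

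*Protocol*

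**What the plan says.** **Women.** In protocol section 5.1, criterion 15a requires contraception from consent, "throughout the study, and for up to 5 months following the last dose of TJ004309". Criterion 15c reads "Avoid conceiving for 5 months after the last dose of TJ004309" and criterion 15d reads "Avoid donation of ova from date of ICF signature until 5 months after the last dose of TJ004309". Section 10.6.6 repeats the 15a period. Exclusion criterion 17 (section 5.2) asks women who are neither sterile nor postmenopausal for contraception during the study and for the same TJ004309-timed 5 months. The synopsis carries copies of the criteria.

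**Men.** Criterion 16 requires condom use "for at least 5 months after the last dose of study treatment, even if he has undergone a successful vasectomy". Section 10.6.7 agrees: "during dose interruptions, and for at least 5 months after the last dose of study" treatment. Exclusion criterion 17 uses the TJ004309 date for men as well: "Male patients must be surgically sterile or must agree to use effective contraception during the study and for 5 months following last dose of TJ004309".

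**Pregnancy reporting.** Section 8.4.8 covers pregnancies in the study or "within 5 months after the patient's last dose of study drug".

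**Which drugs count.** Section 6 names TJ004309 and atezolizumab as the study drugs.

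**The concern.** The plan sets one 5-month precaution but counts it from different dates, and women get the narrower one. The wording also points in opposite directions: *up to* 5 months in 15a and 10.6.6 reads as a ceiling, while *at least* 5 months in criterion 16 is a floor.

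The difference matters only if a woman's last atezolizumab dose falls after her last TJ004309 dose. Her stated obligations could then end less than 5 months after her last study drug, which is shorter than the period the plan sets for men. What is at stake is participant safety and clear counselling and consent wording. No efficacy or safety estimate depends on it.

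**Working it through.** The plan states no figure to reproduce. The check has two steps: whether the two last-dose dates can differ, and how much cover is lost if they do.

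**Step 1. Can the dates differ?**

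| Source | What it indicates |
|---|---|
| Protocol 6.9, Tables 6–8 | Withholding and permanent discontinuation are written for TJ004309 by name; Table 7, for example, discontinues it after a Grade 3 or higher infusion reaction |
| Protocol 6.4 | Atezolizumab is given each 21-day cycle until progression, with modifications per its package insert |
| Protocol 8.4.3 | Causality is judged separately for each drug in the combination |
| SAP 7 and 9.1 | Exposure, and adverse events leading to discontinuation, are reported for each drug |
| Protocol 6.5, Table 5 | All subjects receive the combination; one treatment period is shown for both drugs (contrary indication) |

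So atezolizumab continuing alone is plausible, but it is an inference.

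**Step 2. Cover lost if they differ.** Let T be the last TJ004309 dose, A the last atezolizumab dose, k the number of 21-day atezolizumab cycles given after T (so A − T = 21k), and F the days the woman remains in the study after A. The value of k is an assumption; the documents do not give it. Five months = 5 × 30.4375 = 152.2 days, so the target end of cover is A + 152.2.

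*Contraception (15a, 10.6.6, exclusion 17).* Cover ends at the later of A + F and T + 152.2, so

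shortfall = max(0, min(152.2 − F, 21k)).

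*Ova donation (15d).* The bar ends at T + 152.2 whatever F is, so shortfall = 21k.

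| k | Days left of the TJ004309-timed 5 months after A | Contraception shortfall, F = 90 | Contraception shortfall, F = 30 | Ova-donation shortfall |
|---|---|---|---|---|
| 0 | 152.2 | 0 | 0 | 0 |
| 1 | 131.2 | 21 | 21 | 21 |
| 2 | 110.2 | 42 | 42 | 42 |
| 3 | 89.2 | 62 | 63 | 63 |
| 4 | 68.2 | 62 | 84 | 84 |
| 6 | 26.2 | 62 | 122 | 126 |
| 7 | 5.2 | 62 | 122 | 147 |
| 8 | 0 | 62 | 122 | 168 |

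F = 90 and F = 30 are the two safety follow-up lengths in section 4.5 (30 applies after new anticancer therapy). The contraception caps are 152.2 − 90 = 62.2 and 152.2 − 30 = 122.2 days.

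Those caps assume that being in the study ends with safety follow-up. Longer readings shrink the gap:

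- About 2 years from first dose (section 4.6, synopsis): 730.5 − 152.2 = 578.3, so there is no contraception shortfall if A falls by about day 578.
- About 120 weeks in total, less about 4 weeks of screening (synopsis): 116 × 7 = 812 days and 812 − 152.2 = 659.8, so there is none if A falls by about day 660.

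Section 4.6 follows only subjects without progression when treatment stops, and can end earlier, so neither longer reading covers everyone.

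For ova donation, the bar lapses while atezolizumab is still being given from k = 8 (168 − 152.2 = 15.8 days before the last dose); at k = 7 it does not (147 < 152.2). Criterion 15c also lacks on-study wording, but 15a's contraception duty covers conception while the woman is in the study.

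**The case against.** **The premise is not established.** No text says atezolizumab may continue alone. Section 6.5 and Table 5 describe a combination with one treatment period. The package insert that governs atezolizumab is not among the documents, so an event that stops TJ004309 might stop both drugs. By-drug rows in the SAP fit atezolizumab stopping first equally well, and that leaves no gap. All of this stands and makes every day count conditional. It does not justify a date that works only when the drugs stop together or atezolizumab stops first.

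**The trigger looks uncommon.** Protocol Table 4 shows 13 infusion reactions among 20 Phase 1 patients, none Grade 3 or higher. The exact 95% upper limit for 0 of 20 is 1 − 0.025^(1/20) = 16.8%, so the event is not excluded. This is one trigger only, not a rate of TJ004309 stopping first.

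**Much is already covered.** Contraception is required throughout the study. Section 10.6.8 adds monthly pregnancy testing, although Table 2 schedules no pregnancy test at the 30-, 60- or 90-day visits. A lapse in 15d during dosing needs at least eight atezolizumab-only cycles and a woman with advanced cancer who would donate ova, which is remote.

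**Stronger readings a reader might infer, and why they fail:**

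- *Women may stop contraception while still on atezolizumab.* Not while they are in the study: 15a, 10.6.6 and exclusion 17 prevent that.
- *The men's dates conflict.* All criteria apply together, so the later date in criterion 16 governs.
- *The vasectomy wording is a defect.* Exclusion 17 accepts surgical sterility, and section 10.6.2 treats a man as fertile "unless permanently sterile by bilateral orchidectomy or vasectomy with medical assessment of surgical success", whereas criterion 16 requires condoms regardless. Every inclusion criterion must be met, so criterion 16 governs. Aligning exclusion 17 would be editorial.
- *Five months is too short for atezolizumab.* The documents give no period for that drug, so only the starting date can be questioned.
- *Section 8.4.8 proves that both drugs were meant.* Section 6 supports this, but section 8.7 uses study drug for serum measurements that Table 3 takes for TJ004309 only. This is a reason to spell out the date there too.

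**Conclusion.** The point holds as a minor wording defect. The women's clauses count from TJ004309 alone, although two drugs are given and the men's rule counts from study treatment.

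The size is conditional on atezolizumab outlasting TJ004309. It is zero if both stop together and 21 days per extra cycle otherwise. For contraception the loss falls only after the woman leaves the study. It is capped at about 62 or 122 days if that is the end of safety follow-up, and is often zero if participation runs longer. For ova donation there is no cap. The frequency of the situation cannot be estimated from the documents. No estimate, error rate or analysis is affected.

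**What to change.** In criteria 15a, 15c and 15d, exclusion criterion 17 (women), section 10.6.6 and the synopsis copies, set the end point as *at least 5 months after the last dose of TJ004309 or atezolizumab, whichever is later*, and delete *up to* where it appears. For consistency, put the same end point in exclusion criterion 17 for men and in section 8.4.8.

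The cost is protocol, synopsis and consent wording. Visits, sample size and analyses do not change. SAP section 4.1 records that Part 2 was not initiated, so the practical benefit is limited to any patients still within the post-dose window and to later protocols that reuse this text.
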